### **8.3 Missing Data**

All missing data due to early discontinuation of participants from the study or otherwise will be handled using mixed-effects modeling (i.e., multilevel modeling) with participant random intercepts. Multilevel models yield unbiased and consistent estimates of model parameters of interest in the presence of missing outcomes under either Missing Completely at Random or Missing at Random missing data mechanisms. Sensitivity to this assumption will be assessed by comparing analytic results using the modified intention to treat sample to complete-case analyses. Complete-case analyses yield unbiased and consistent estimates under a Missing Completely at Random missing data mechanism, although they are less efficient due to the removal of participant data.

Study personnel will make concerted efforts to follow-up with participants that prematurely discontinue participation in the study to understand potential reasons for their discontinuation where possible.

Participant retention and attrition will be summarized at each primary assessment point in the study (Baseline, Post-Intervention, and 1-Month Follow-Up).

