**8      General Analysis Considerations****8.1    Analysis Populations****8.1.1    Modified Intention to Treat Population**

All subjects who received any study drug and who participated in at least one post-baseline assessment (i.e., all randomized participants with data following the treatment intervention window).

Participants may be removed from the Modified Intention to Treat Population for analysis if they have (a) no observed data on Post-Intervention assessments, (b) withdrew consent during the study, or (c) were unable to access the online intervention and daily emotion reporting platform.

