## 10 Efficacy Analyses

All efficacy variables will be summarized by treatment group in accordance with Section 9.

Except for the two Daily Survey Measures [Change in Affective Reactivity to Stress as Measured by the Daily Modified Differential Emotions Scale (mDES) and Change in Affective Reactivity to Stress as Measured by the Daily Inventory of Stressful Events (DISE)], all Secondary Outcomes will be analyzed using mixed-effects analysis of variance with treatment group by time (Post-Intervention, 1-Month Follow-Up) adjusting for the mean-centered Baseline scores on the respective secondary outcome. Models will include fixed effects for treatment (LARKSPUR vs. control), time (Post-Intervention, 1-month Follow-Up), and the interaction between treatment and time. Random intercepts for participants will be included to account for within-participant correlation over time. The modified Intention-to-Treat sample described in Section 8.1 will be used. Treatment groups will be compared at Post-Intervention, at 1-Month Follow-Up, and with respect to their change from Post-Intervention to 1-Month Follow-Up using 2-sided tests at the 5% significance level under the null hypothesis of no difference in means/change. All assumptions for the mixed-effects models will be assessed by inspection of plots of within-participant and between-person residuals. Standard errors, degrees of freedom, 95% confidence intervals, and p-values will be adjusted using the Kenward-Roger method to control the significance level [4]. Restricted maximum likelihood (REML) estimation will be used. All analyses are exploratory with the aim of hypothesis generation as described in the Study Protocol given the pilot nature of this study.

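### The SAP's one sensitivity analysis of the effect estimates, modified ITT against complete cases, cannot test missing at random for participants lost before Post-Intervention who do not return

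*SAP*

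**What the plan says.** SAP 8.3 states that "All missing data due to early discontinuation of participants from the study or otherwise will be handled using mixed-effects modeling", with participant random intercepts, and that such models are valid under MCAR or MAR. It then gives the test of that assumption: "Sensitivity to this assumption will be assessed by comparing analytic results using the modified intention to treat sample to complete-case analyses". The same section says that complete-case analysis is unbiased under MCAR. No analysis under missing not at random (MNAR) is named.

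SAP 8.1.1 defines the modified ITT set as "All subjects who received any study drug and who participated in at least one post-baseline assessment". It adds that participants may be removed if they have "no observed data on Post-Intervention assessments", withdrew consent, or "were unable to access the online intervention and daily emotion reporting platform".

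SAP 10 models the survey outcomes by "treatment group by time (Post-Intervention, 1-Month Follow-Up) adjusting for the mean-centered Baseline scores". Post-Intervention and 1-Month scores are the outcomes, and Baseline is a covariate. The two daily-survey models in SAP 10.2.1 do take Baseline as an outcome time, but they use the same modified ITT set.

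Elsewhere, SAP 10.1 tests retention between arms, SAP 8.3 and 9.1 summarise attrition and its reasons, and Protocol Section 8 promises, in general terms, to assess missingness and impute.

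**The concern.** A sensitivity analysis for MAR should ask what happens to the estimate if MAR fails. This one replaces the main analysis with another that rests on a stronger assumption and drops more people. Participants with no post-baseline data are on neither side of the comparison, so their absence cannot make the two results differ.

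This matters because the second objective (Protocol 1.1.1, SAP 5.1.1.2) is to estimate an effect size as groundwork for a larger trial. Allocation is open and outcomes are self-reported. Burden differs between arms: Protocol Section 3 gives about 5 minutes a day in control, and the same check-in plus lessons and home practice in LARKSPUR. Early departure linked to lack of benefit is plausible. If it occurs, close agreement between the two planned analyses would be read as support for MAR when it carries no information about those people.

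**Working it through.** **1. Who is in each set.** The SAP does not define a complete case; I take it to need both follow-up scores.

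| Follow-up data | Modified ITT | Complete cases |
|---|---|---|
| Both visits | in | in |
| Post-Intervention only | in | out |
| 1 month only | in, unless removed at discretion | out |
| Neither | out | out |

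The two analyses can differ only through the middle rows. Someone in the last row is excluded by definition in 8.1.1. Even if readmitted, that person adds nothing to the Section 10 likelihood, because no outcome is observed.

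**2. The plan's own attrition figure.** SAP 7 recruits 45 per group for a target of 30, which implies 1 − 30/45 = 33% loss. SAP 7 gives no rate and ties the allowance to the interval from end of trial to follow-up. It is therefore not a figure for loss before Post-Intervention. Protocol Section 3 reports retention of about 80% with the control condition in past research, so 20% is used below as an assumption for early loss.

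**3. Size of what the check cannot see.** Let p be the share lost early in an arm and delta the departure of their outcome from its MAR prediction. Then

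shift in all-randomised effect = p(LARKSPUR) × delta(LARKSPUR) − p(control) × delta(control).

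With control at its MAR prediction and p = 0.20 in LARKSPUR:

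- delta 0.2 SD: 0.20 × 0.2 = 0.04 SD
- delta 0.5 SD: 0.20 × 0.5 = 0.10 SD
- delta 0.8 SD: 0.20 × 0.8 = 0.16 SD

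**4. Simulation of the two planned analyses.** There were 2,000 trials per setting, using the Section 10 model with REML. Assumptions: SD 1, correlation 0.6 between visits, no true effect, lower scores better, equal share lost in each arm, control loss random. In the early-loss rows, 15% of those remaining also miss 1 month at random. Kenward-Roger does not change point estimates and was left out. Results are for 45 per arm, in SD, Post-Intervention / 1 month:

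| Loss in LARKSPUR | Share | Bias of modified ITT | Modified ITT minus complete case |
|---|---|---|---|
| Early, depends on unseen Post-Intervention score (MNAR) | 20% | −0.16 / −0.06 | 0.00 / 0.00 |
| Early, depends on Baseline only | 20% | 0.00 / 0.00 | 0.00 / 0.00 |
| Early, random | 20% | 0.00 / −0.01 | 0.00 / 0.00 |
| Late, depends on Post-Intervention score (MAR) | 20% | 0.00 / 0.00 | 0.16 / 0.06 |
| Same | 33% | 0.00 / 0.00 | 0.25 / 0.10 |
| Late, depends on unseen 1-month score (MNAR) | 20% | 0.00 / −0.13 | 0.06 / 0.02 |
| Same | 33% | 0.00 / −0.20 | 0.10 / 0.04 |

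At 75 per arm (Protocol Section 3; the SAP has 45) every entry agrees within 0.01.

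**5. Reading the table.** In the three early-loss rows the check averages 0.00, and its trial-to-trial SD at Post-Intervention is about 0.08 in each (0.06 at 75 per arm). It looks the same whether the estimate is biased or not. The bias of 0.16 corresponds to delta = 0.16/0.20 = 0.8 SD, so that row is the top of the range in step 3. For late MAR loss the check moves by 0.16 to 0.25 SD at Post-Intervention although the main analysis is sound. For late MNAR loss it moves by 0.02 to 0.04 SD at 1 month against a bias of 0.13 to 0.20 SD.

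**The case against.** Four points on the other side have force.

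- **The mixed model is not at fault.** A reader might infer that SAP 8.3 is simply wrong to say the model deals with early discontinuation. That goes too far. If early loss depends only on arm and Baseline, leaving out people without outcomes causes no bias, as the second and third rows show. The sentence needs its MAR condition attached, not deletion.
- **Dropout is not ignored.** The retention test, the attrition summaries, the reasons for leaving and the Protocol's imputation sentence all stand. They describe loss, or promise a method that the SAP does not then specify; none measures bias in an effect. Equal retention does not settle it either, because delta can differ between arms.
- **The check is not empty.** For loss after Post-Intervention it can reveal departure from MCAR. Removal for missing Post-Intervention data is also discretionary, so someone who returns at 1 month may be kept.
- **This is an exploratory pilot.** With 45 × 0.80 = 36 per arm and the residual SD √(1 − 0.6²) = 0.8 assumed above, the 95% half-width at one visit is about 1.96 × 0.8 × √(2/36) = 0.37 SD. With 75 × 0.80 = 60 it is 0.29 SD. Shifts of 0.04 to 0.16 SD lie inside that. This limits the weight of the point, but the interval does not include bias, and nothing in the report would signal it.

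**Conclusion.** The point holds in this form: the only prespecified sensitivity analysis of the effect estimates cannot test MAR for participants lost before Post-Intervention who do not return. For later loss it is weak against MNAR and can signal a difference when the MAR model is sound. This follows from SAP 8.1.1, 8.3 and 10 and needs no simulation.

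The size is illustrative only: 0.04 to 0.16 SD at an assumed 20% early loss in LARKSPUR and delta of 0.2 to 0.8 SD, with control at its MAR prediction. The documents give no planned early-loss rate, effect size or delta.

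A reader might go further and infer that the effect will be overstated by 25%, or by 50% using the 45-for-30 allowance. Those figures are only 1/0.80 − 1 and 1/(30/45) − 1. They assume no effect at all in leavers, and the second also moves an allowance for later attrition to before Post-Intervention. The documents support neither.

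The consequence is for how far the effect size can be carried into planning the larger trial. No confirmatory conclusion is affected.

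**What to change.** Amend SAP 8.3, for pain intensity and pain interference at least:

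1. Replace complete-case analysis as the test of MAR with multiple imputation over all randomised participants who have a Baseline score and whose data may be used under their consent. Include arm, Baseline and both follow-up scores in the imputation model. Adding these people to the Section 10 model alone would change nothing.
2. Apply a delta shift, set separately by arm and over a range stated in advance, to participants without follow-up data. Report the tipping point and say how it is defined. If only LARKSPUR is shifted, the estimate reaches zero at about delta = MAR estimate / p, which is five times the estimate at p = 0.20. Reference-based imputation from control is an optional further scenario.
3. Keep the complete-case result as descriptive, and define a complete case.
4. Qualify the mixed-model sentence: for participants with no follow-up scores, it handles early discontinuation only under MAR given arm and Baseline.

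The cost is SAP wording and one extra exploratory sensitivity analysis on data already collected. Its estimates will probably be smaller, with wider intervals. It would also give content to the imputation promised in Protocol Section 8.

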### **8.4 Multiple Testing**

Because this is a pilot study for the purpose of establishing feasibility, control of the overall study-wide significance level is of lesser concern. However, it is important to reflect the statistical uncertainty in analytic results. Accordingly, analytic results will present confidence intervals alongside treatment effect estimates and p-values where appropriate. Kenward-Roger adjustments to the corresponding standard error estimates, degrees of freedom, confidence intervals, and p-values will be used for the multilevel model analyses of secondary outcomes to control the significance level [4].

## **9 Summary of Study Data**

Feasibility and acceptability will be examined by conducting frequency and descriptive statistics (i.e., non-missing sample size, mean, median, standard deviation, maximum, minimum) for enrollment rates, number of sessions completed, number of weeks required to complete the intervention, and Likert-scale items assessing satisfaction with the intervention and perceived helpfulness. Generally, all data will be summarized by treatment and visit number within subject. All summary tables will be structured with a column for each treatment in the order (Control, Experimental) and will be annotated with the total population size relevant to that table/treatment, including any missing observations. Note that the sample size of non-missing values for univariate summary statistics may be larger than the sample size of non-missing values in a complete-case analysis, as different participants may have missing values in different variables, such as baseline covariates and the endpoints.

### **9.1 Subject Disposition**

[figure not shown]
Enrollment at Baseline and Retention at Post-Intervention and 1-month Follow-Up will be established as described in Section 6.4.

Reasons for participant exclusion during enrollment will include failure to meet inclusion criteria (see Section 6.2), unwillingness to provide informed consent, etc.

Reasons for participant attrition may include withdrawal of consent, disrupted technological access, non-responsiveness during the intervention period on the intervention platform, or failure to complete Post-Intervention or 1-Month Follow-Up assessments.

Participant disposition summary statistics will be produced in accordance with Section 9.

A skeleton CONSORT flow diagram is provided below.

**Table 2.** Study CONSORT flow diagram

## **9.2 Demographic and Baseline Variables**

### **9.2.1 Demographic Variables**

#### **9.2.1.1 Age**

50-59 years, 60-69 years, 70-79 years, ≥ 80 years)

#### **9.2.1.2 Sex**

Male, Female

#### **9.2.1.3 Ethnicity**

NIH/OMB Categories: Hispanic or Latino, Not Hispanic or Latino, Unknown or Not Reported

#### **9.2.1.4 Race**

NIH/OMB Categories: American Indian or Alaska Native, Asian, Native Hawaiian or Other Pacific Islander, Black or African American, White, More than one race, Unknown or Not Reported

## **9.2.2 Baseline Variables**

### **9.2.2.1 PROMIS Pain Intensity Short Form 3a**

### **9.2.2.2 PROMIS Pain Interference Short Form 6b**

### **9.2.2.3 PROMIS Physical Functioning Short Form 10a**

### **9.2.2.4 PROMIS Fatigue Short Form 6a**

### **9.2.2.5 Change in Depressive Symptoms as Measured by the Center for Epidemiologic Studies Depression Scale Revised (CESD-R-10)**

### **9.2.2.6 Change in Stress Appraisal as Measured by the Perceived Stress Scale**

### **9.2.2.7 Change in Positive Affect as Measured by the Modified Differential Emotions Scale (mDES)**

### **9.2.2.8 Change in Positive Affect as Measured by the Positive and Negative Affect Scale (PANAS-GEN)**

### **9.2.2.9 Change in Affective Reactivity to Stress as Measured by the Daily Modified Differential Emotions Scale (mDES)**

### **9.2.2.10 Change in Affective Reactivity to Stress as Measured by the Daily Inventory of Stressful Events (DISE)**

The summary statistics will be produced in accordance with Section 9.

## **9.3 Concurrent Illnesses and Medical Conditions**

Chronic comorbid medical conditions will be assessed using an interviewer-administered version of the Charlson Comorbidity Index [14].

## 10 Efficacy Analyses

All efficacy variables will be summarized by treatment group in accordance with Section 9.

Except for the two Daily Survey Measures [Change in Affective Reactivity to Stress as Measured by the Daily Modified Differential Emotions Scale (mDES) and Change in Affective Reactivity to Stress as Measured by the Daily Inventory of Stressful Events (DISE)], all Secondary Outcomes will be analyzed using mixed-effects analysis of variance with treatment group by time (Post-Intervention, 1-Month Follow-Up) adjusting for the mean-centered Baseline scores on the respective secondary outcome. Models will include fixed effects for treatment (LARKSPUR vs. control), time (Post-Intervention, 1-month Follow-Up), and the interaction between treatment and time. Random intercepts for participants will be included to account for within-participant correlation over time. The modified Intention-to-Treat sample described in Section 8.1 will be used. Treatment groups will be compared at Post-Intervention, at 1-Month Follow-Up, and with respect to their change from Post-Intervention to 1-Month Follow-Up using 2-sided tests at the 5% significance level under the null hypothesis of no difference in means/change. All assumptions for the mixed-effects models will be assessed by inspection of plots of within-participant and between-person residuals. Standard errors, degrees of freedom, 95% confidence intervals, and p-values will be adjusted using the Kenward-Roger method to control the significance level [4]. Restricted maximum likelihood (REML) estimation will be used. All analyses are exploratory with the aim of hypothesis generation as described in the Study Protocol given the pilot nature of this study.

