**8.2    Covariates and Subgroups**

Baseline covariates for each secondary outcome are expected to correlate with their matching secondary outcome scores at Post-Intervention and 1-Month Follow-Up assessments. Therefore, analyses of each secondary outcome will include participant Baseline scores for adjustment of superiority analyses of treatment differences.

Race/ethnicity was used to stratify treatment allocation and will be adjusted for in primary analyses if sample sizes within each race/ethnicity—treatment subgroup is sufficient (i.e., greater than 5). Otherwise, race/ethnicity will be omitted from primary analyses.

Given the pilot nature of the study, sample size was chosen based on feasibility indicators (recruitment, retention, adherence) rather than on formal power calculations [see 1]. Accordingly, interaction analyses comparing treatment effects by race/ethnicity, age and gender are exploratory.

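### The survey-outcome model pools the residual variance and the Baseline slope across the two follow-up visits, so the visit-specific intervals are miscalibrated if the Baseline-adjusted variances differ

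*SAP*

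**What the plan says.** SAP Section 10 covers every secondary outcome except the two daily-survey measures. Only Post-Intervention and 1-Month Follow-Up are outcome visits. Baseline enters as a covariate, the analysis "adjusting for the mean-centered Baseline scores on the respective secondary outcome". The rest of the mean model is: "Models will include fixed effects for treatment (LARKSPUR vs. control), time (Post-Intervention, 1-month Follow-Up), and the interaction between treatment and time". The covariance is described in one sentence: "Random intercepts for participants will be included to account for within-participant correlation over time". No Baseline-by-time term, visit-specific residual variance or unstructured covariance is mentioned.

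Three contrasts follow: "Treatment groups will be compared at Post-Intervention, at 1-Month Follow-Up, and with respect to their change from Post-Intervention to 1-Month Follow-Up", each "using 2-sided tests at the 5% significance level under the null hypothesis of no difference in means/change". Estimation is by REML, and "Standard errors, degrees of freedom, 95% confidence intervals, and p-values will be adjusted using the Kenward-Roger method to control the significance level". On model checking the SAP says: "All assumptions for the mixed-effects models will be assessed by inspection of plots of within-participant and between-person residuals". It states no action if the plots look poor.

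Section 8.2 gives the reason for the adjustment: "Baseline covariates for each secondary outcome are expected to correlate with their matching secondary outcome scores at Post-Intervention and 1-Month Follow-Up assessments". It gives no values and does not say that the two correlations are equal. Section 8.3 names the same participant random intercept as the way missing data are handled.

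**The concern.** A participant random intercept over two visits is compound symmetry: one variance, one covariance. With a single Baseline slope, the model also assumes that Baseline predicts both visits equally well. In complete data it therefore gives the Post-Intervention and 1-Month contrasts the same standard error. If the true Baseline-adjusted variances differ, that standard error is too large at one visit and too small at the other.

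The visit-specific estimates and intervals are what Aim 2 delivers for pain and the other seven survey outcomes. SAP Section 8.4 relaxes study-wide error control but relies on confidence intervals to convey uncertainty, so their calibration matters even in a pilot. None of the planned safeguards prevents the problem. Kenward-Roger is a small-sample adjustment within the assumed covariance. The complete-case comparison in Section 8.3 changes the sample, not the covariance. The residual plots have no prespecified consequence.

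**Working it through.** **Inputs.** From the SAP: 1:1 allocation, 5% two-sided tests, 45 per arm (Section 7). From the Protocol: 75 per arm (Section 3, Randomization). Assumed, because neither document gives them: SD 1 at Baseline and Post-Intervention, SD s at 1-Month, and Baseline correlations r1 (Post-Intervention) and r2 (1-Month).

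**Formulas (complete data, large sample).**
- Visit slopes: b1 = r1, b2 = s·r2. The common slope estimates b = (b1 + b2)/2.
- True variances about the common slope: vPost = 1 − 2·b·b1 + b² and v1M = s² − 2·b·b2 + b².
- The planned model uses vPool = (vPost + v1M)/2 at both visits.
- True size at a visit with variance v: 2·[1 − Φ(1.96·√(vPool/v))].

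**The plan's own figure.** At r1 = r2 = 0.70 and s = 1, vPost = v1M = vPool = 0.51, and size is 5.0% at both visits. The nominal level is reproduced when the equality assumptions hold.

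**Worked case, r1 = 0.70, r2 = 0.55, s = 1.** b = 0.625; vPost = 1 − 0.875 + 0.3906 = 0.5156; v1M = 1 − 0.6875 + 0.3906 = 0.7031; vPool = 0.6094. The ratio of model to true standard error is √(0.6094/0.5156) = 1.087 at Post-Intervention and √(0.6094/0.7031) = 0.931 at 1-Month. Size is 3.3% and 6.8%.

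| r1 / r2 | s | Size at Post-Intervention | Size at 1-Month |
|---|---|---|---|
| 0.70 / 0.70 | 1 | 5.0% | 5.0% |
| 0.65 / 0.60 | 1 | 4.4% | 5.6% |
| 0.70 / 0.60 | 1 | 3.8% | 6.3% |
| 0.70 / 0.55 | 1 | 3.3% | 6.8% |
| 0.70 / 0.50 | 1 | 3.0% | 7.2% |
| 0.70 / 0.55 | 0.8 | 5.7% | 4.3% |

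**Direction.** Subtracting the two variances gives v1M − vPost = s²(1 − r2²) − (1 − r1²). The 1-Month interval is the narrow one only if s exceeds √[(1 − r1²)/(1 − r2²)]. That threshold is √(0.51/0.6975) = 0.86 at 0.70/0.55 and √(0.51/0.75) = 0.82 at 0.70/0.50.

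**Power at Post-Intervention, 0.4 SD effect, 0.70/0.55, s = 1.** Planned model: Φ[(0.4 − 1.96·SEmodel)/SEtrue]. With visit-specific slope and variance, the residual variance is 1 − 0.70² = 0.51 and power is Φ[0.4/SE − 1.96].
- 45 per arm: SEmodel = √(2·0.6094/45) = 0.1646 and SEtrue = √(2·0.5156/45) = 0.1514, giving 70%. With the change, SE = √(2·0.51/45) = 0.1506, giving 76%.
- 75 per arm: 0.1275 and 0.1173, giving 90%. With the change, SE = 0.1166, giving 93%.

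**Simulation check.** 4,000 trials, 45 per arm, 0.70/0.50, equal SDs, REML with Satterthwaite-type degrees of freedom standing in for Kenward-Roger. The planned model covers 96.8% at Post-Intervention and 92.7% at 1-Month, or 97.2% and 92.6% with 20% missing at random positions at 1-Month. Unstructured covariance plus Baseline-by-time covers 94.8% and 95.0% (95.4% at both visits with the missing data). The half-width changes from 0.334 SD at both visits to 0.300 SD at Post-Intervention and 0.364 SD at 1-Month. Coverage of the change contrast under the planned model stays near 95% (95.1% complete, 94.4% with missing data).

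**The case against.** The strongest reply is that the distortion rests on inputs the documents do not supply. Post-Intervention falls about 8 weeks after Baseline and the follow-up one month later. Even pure exponential decay from 0.70 at 8 weeks gives 0.70^1.5 = 0.59 at 12 weeks, and any stable trait component would hold the correlation higher. On that view 0.50 and 0.55 are steep, and the realistic distortion is about one percentage point of size at each visit. The SAP also calls these analyses exploratory, both documents say the trial is not powered for outcome differences, and residual plots by participant could show unequal variances. All of this stands and limits the importance of the point. It does not supply a remedy if the plots do show a difference.

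A reader might infer that the Post-Intervention interval must be too wide and the 1-Month interval too narrow. The documents do not support that: no SDs are given, and the direction reverses if the 1-Month SD is low enough. A reader might also infer that the treatment estimates are biased. In randomised complete data a common Baseline slope leaves the contrasts unbiased; only their stated precision is wrong. Nor does main-trial planning depend on the pooled variance, since SAP Section 9 calls for SDs by treatment and visit.

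**Conclusion.** The point holds in conditional form. The Section 10 model ties both visit-specific contrasts to one pooled residual variance. If the Baseline-adjusted variances differ, one interval is too wide and the other too narrow, and neither Kenward-Roger nor a larger sample removes the discrepancy. Under the equal-SD correlations tried, size moves by roughly 0.6 to 2 percentage points, and at 0.70/0.55 power at Post-Intervention falls by about 6 points at 45 per arm or 3 at 75. With equal correlations and SDs there is no distortion. The change contrast is essentially unaffected in the case simulated. The mechanism is certain from the text; the size and direction rest on assumed correlations and SDs. For an exploratory pilot this lies between an optional and a recommended change.

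**What to change.** In SAP Section 10, for the eight survey outcomes, replace the participant random intercept by an unstructured 2x2 within-participant covariance for Post-Intervention and 1-Month, and add a Baseline-by-time fixed effect. Keep REML and Kenward-Roger. Amend Section 8.3, which separately prescribes participant random intercepts, so that the two sections agree for these outcomes.

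The cost is SAP wording, one more covariance parameter and one more fixed effect. The interval at the more variable visit becomes somewhat wider (about 9% at 1-Month in the simulated 0.70/0.50 case, with Post-Intervention about 10% narrower). Where the plan's equality assumptions hold, almost nothing changes: in the simulated 0.70/0.70 case the half-widths were 0.298 SD as planned and 0.299 to 0.300 SD with the change.
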